4.2.5 Primary safety analysis

4.2.5.1 AEs and SAEs

AEs will be summarized using Medical Dictionary for Regulatory Activities (MedDRA) System Organ Class and preferred terms. Tables will show by treatment arm the number and percentage of participants experiencing an AE within a System Organ Class or within preferred term category by severity or by relationship to treatment interruption. For the calculations in these tables, a participant with multiple AEs within a category will be counted once under the maximum severity or the strongest recorded causal relationship to treatment interruption. Formal statistical testing comparing arms is not planned since interpretation of differences must rely heavily upon clinical judgment.

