6.1.2 Enrollment

- Participants undergoing an “ART switch” will be considered enrolled on the first day of the new ART medication.
- Participants who do not undergo an “ART switch” will be considered enrolled at the initiation of ATI (Day 0).

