11.2.3 AE reporting

An AE is any untoward medical occurrence in a clinical investigation participant, including an abnormal laboratory finding, symptom, or disease temporally

associated with the individual's participation in the research, whether or not related to the research.

The study intervention for which adverse event attribution reporting is required is ATI.

At designated visits, information regarding AEs will be elicited by appropriate questioning and examinations and will be documented in the medical record and in the electronic database.

All AEs are graded according to the Division of AIDS (DAIDS) Table for Grading the Severity of Adult and Pediatric Adverse Events, Corrected Version 2.1, July 2017, available on the DAIDS Regulatory Support Center (RSC) website at <https://rsc.niaid.nih.gov/clinical-research-sites/daids-adverse-event-grading-tables>, except:

- Unintentional Weight Loss is required to be reported as an AE only if it is considered to be potentially deleterious to the participant's health (see HVTN 805/HPTN 093 SSP); and
- Creatinine is required to be reported as an AE only if it is gradable per the increase from local lab upper limit of normal (ULN) parameter. Do not grade elevated creatinine based on the change from the baseline parameter.
- eGFR is required to be reported as an AE only if it is gradable per reported value or if dialysis is needed. Do not grade decreased eGFR based on the change from the baseline parameter (see HVTN 805/HPTN 093 SSP).

All AEs are reported to the SDMC on the appropriate CRF.

Sites are expected to notify HVTN clinical safety staff of any serious safety concern requiring their attention. Telephone numbers and email addresses are found on the protocol home page on the HVTN Members' site (<https://members.hvtn.org/protocols/hvtn805-hptn093>). Concerns requiring immediate attention should be communicated by calling the clinical safety phone. In the case of email notification, clinical safety staff will reply within one business day.

In addition, CRS investigators are required to submit AE information in accordance with IRB/EC and any applicable RE requirements.

12 Ethics/protection of human subjects

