10 SAFETY TABLES, PARTICIPANT LISTINGS, AND FIGURES

10.1 List of Tables

The following tables are included in the DSMB reports and FSR for Safety:

- Enrollment by study site
- Baseline participant characteristics
- Study status and reasons for early termination

- Visit retention, Schedule 1
- Visit retention, Schedule 2
- Visit retention, Schedule 3
- Reasons for meeting ART re-initiation criteria
- Summary of time to meeting ART re-initiation criteria
- Turnaround times for ART Re-Initiation
- SAE listing
- STI listing
- Grade 1-5 Adverse Events by System Organ Class, Ordered by Decreasing Frequency
- Grade 3+ Adverse Events by System Organ Class, High Level Term, and Severity
- Grade 1-5 Adverse Events Related to ATI by System Organ Class, High Level Term, and Severity
- Pregnancy listing

Additional tables include in the FSR for Safety:

- Local Lab Value Summary Statistics
- Local Laboratory Values Meeting Grade 2 AE Criteria or Above

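### The AE tables for the safety-of-ATI objective have no analysis period and no person-time, so they give no AE rate for time off ART

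*Protocol*

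**What the plan says.** Protocol 4.2.5.1, repeated in SAP 6.5, sets the AE summary: "Tables will show by treatment arm the number and percentage of participants experiencing an AE within a System Organ Class". The breakdown is by grade or by attribution to ATI, at class or preferred-term level, and not by study phase. On counting, "a participant with multiple AEs within a category will be counted once under the maximum severity or the strongest recorded causal relationship". On the arms, "Formal statistical testing comparing arms is not planned since interpretation of differences must rely heavily upon clinical judgment".

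SAP 10.1 lists the AE tables for the DSMB reports and the final safety report. They include "Grade 1-5 Adverse Events by System Organ Class, Ordered by Decreasing Frequency", a Grade 3+ table and a table of AEs related to ATI. None of these titles or texts names a period, a schedule or a time denominator.

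Collection is wide. Protocol 11.2.3 takes in untoward occurrences "associated with the individual's participation in the research, whether or not related to the research". Participants who change regimen "will be considered enrolled on the first day of the new ART medication", which is before ATI begins. AE assessment appears in the procedures for the ART switch (6.1.3), ATI (6.1.4 and 6.2) and Schedule 3 (6.3), and Appendix J carries it to week 52. Attribution, by contrast, is narrow: "The study intervention for which adverse event attribution reporting is required is ATI".

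**The concern.** Protocol 4.1.2 states that the safety evaluation is meant to identify concerns associated with ATI. For that, the reader needs to know how often AEs occur while participants are off ART. A count-once percentage over an unspecified window does not say so, for three reasons.

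- If the window is the whole study, most of it is time on ART, and a higher AE rate off ART is diluted.
- The count-once rule discards timing. A participant with the same event off ART and again back on ART appears once.
- Time off ART ends at the efficacy endpoint. If VRC01 delays that endpoint, as the primary hypothesis proposes, VRC01 recipients are exposed to ATI for longer and collect more AEs at the same rate.

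The SAP does split other outputs by phase. Visit retention is tabulated separately for Schedules 1, 2 and 3 (SAP 10.1). One viral load and CD4+ figure is restricted to Schedule 1 and 2 data, and laboratory box plots are listed by schedule and visit (SAP 10.2). The AE tables have no such restriction. At best, the period is left to be chosen after data are seen.

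**Working it through.** **Inputs.** Time to re-initiation criteria: Weibull, S(t) = exp[-(λt)^p], λ = exp(-2.932), p = 2.014 (protocol 4.1.1). Censoring is exponential at 20% per year, taken as c = -ln(0.8)/52 per week, with a 72-week maximum (same section). Schedule 3 lasts 52 weeks (Appendix J). Background AE rate: none is given, so 0.2 to 2 first events per person-year is assumed. The doubling off ART is also assumed.

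**The plan's own figures.** The median is ln(2)^(1/p)/λ = 15.64 weeks (stated: 15.6). Median increases θ^(-1/p) - 1 for hazard ratios 0.6, 0.5, 0.4 and 0.3 are 29%, 41%, 58% and 82%, as stated. Protocol Table 4-2, all enrolled, n = 16/39/61: 1 - 0.1^(1/n) = 13.4%/5.7%/3.7%, as printed.

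**Mean time off ART.** The integral over 0 to 72 weeks of exp[-HR(λt)^p - ct] gives:

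- placebo (HR 1): 15.9 weeks, and 15.9/(15.9 + 52) = 23% of ATI plus Schedule 3 time;
- VRC01 at HR 0.4: 24.4 weeks, and 24.4/(24.4 + 52) = 32%.

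**Dilution, placebo group.** With X the time off ART in weeks and r the background rate per year, the share with an AE during ATI is E[1 - exp(-krX/52)], where k = 1 (no effect) or k = 2 (doubled off ART). Pooled with 52 weeks on ART at rate r, it is E[1 - exp(-krX/52 - r)].

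| r per year | ATI period, k=1 to k=2 | ratio | pooled, k=1 to k=2 | ratio |
|---|---|---|---|---|
| 0.2 | 5.9% to 11.3% | 1.92 | 22.9% to 27.4% | 1.19 |
| 0.5 | 13.9% to 25.4% | 1.83 | 47.8% to 54.7% | 1.15 |
| 1 | 25.4% to 42.9% | 1.69 | 72.5% to 79.0% | 1.09 |
| 2 | 42.9% to 64.3% | 1.50 | 92.3% to 95.2% | 1.03 |

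**Arms at the same AE rate.** With r = 1 in both arms and HR 0.4, ATI-period percentages are 25% (placebo) and 35% (VRC01), from exposure alone. Pooled they are 72.5% and 76.3%, a gap of about 4 points.

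**Time base of Table 4-2.** A 90% chance of at least one event needs about ln(10)/n expected events per participant. For n = 61 this is 2.303/61 = 0.0377. Over 15.9 weeks that is 0.0377/(15.9/52), about 12.3 per 100 person-years. Over 67.9 pooled weeks it is about 2.9. For n = 16 the figures are about 47 and 11. The table does not say which period it means.

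**Off-ART versus on-ART rate ratio.** Assume 17 weeks off ART at 2 per year and 52 weeks on ART at 1 per year. The standard error of the log ratio is √(1/events off + 1/events on). For N = 40, with 26.2 and 40 events, the ratio 2.0 has a 95% CI of 1.2 to 3.3. For N = 16, with 10.5 and 16 events, it is 0.92 to 4.36. Both ignore clustering within participants.

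**The case against.** **Pooling is not stated.** A reader might infer that the plan commits to one percentage per arm over the whole study. It does not. No text combines the phases; the window is simply not given. This stands, and it is why the dilution figures are conditional on reading the tables as covering all collected AEs.

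**Safety is not judged from these percentages alone.** Primary endpoint 2 also covers laboratory measures, SAEs and discontinuations. The SAP plans a table of AEs related to ATI; listings of SAEs, STIs and pregnancies; and participant-level viral load and CD4+ plots. Grade 2+ laboratory values are tabulated at each timepoint after ATI starts (protocol 4.2.5.2). The PSRT reviews safety twice a month and watches for failure to re-suppress (11.1.1), and the DSMB also reviews (11.1.2). All of this reduces the risk of missing a harm. However, the related-AE table depends on attribution in a study with no concurrent group staying on ART, listings carry no denominator, and the DSMB receives the same AE tables.

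**The arm contrast is secondary.** A reader might conclude that the arms are not comparable, or that VRC01 will be made to look unsafe. The documents do not support either. No arm test is planned, no product is given in this study, and attribution is to ATI. The exposure gap arises only if VRC01 prolongs control. The 25% versus 35% gap belongs to an ATI-only table; pooling shrinks it to about 4 points.

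**A rate ratio of time off ART to time on ART is not a clean contrast.** Appendix K schedules 12 post-baseline visits in the first 16 weeks of ATI, and 12 in the 52 weeks of Schedule 3. Hematology and chemistry are every 4 weeks for much of ATI but every 12 weeks late in Schedule 3, and some Schedule 3 STI tests are waived once viral load is undetectable. Schedule 3 always follows ATI and may carry its late effects. The ratio could exceed 1 from ascertainment alone. This stands in full and limits the remedy.

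**Conclusion.** The point holds as a gap in the AE analysis: no period, no person-time, and therefore no AE rate for time off ART, which is what primary objective 2 needs. Read as covering all collected AEs, the tables would show a true doubling off ART as a ratio of 1.03 to 1.19, against 1.50 to 1.92 in an ATI-period table. If control is prolonged at HR 0.4, mean time off ART differs by arm (15.9 against 24.4 weeks), so ATI-period percentages also need a time denominator.

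These sizes rest on the protocol's time and censoring model, the assumed background rates, and a full 52 weeks of Schedule 3 for everyone. If some leave Schedule 3 early, the dilution is smaller. The model stops the clock at the criteria, so it leaves out any delay before ART is restarted. The documents do not support the stronger claims that safety rests on crude percentages alone or that the planned outputs could not reveal a harm. It is a change that should be made, in the reporting rather than the design.

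**What to change.** In SAP 6.5 and 10.1, define three AE periods: ART switch, off ART (Schedules 1 and 2), and back on ART (Schedule 3), with a rule assigning each event by onset date. For all AEs, Grade 3+ AEs and SAEs, add by period, by arm and overall: participants with an event, number of events, person-years, and the rate per 100 person-years with a 95% CI. Keep the existing tables. State the time base of Table 4-2.

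If a rate ratio of time off ART to time on ART is shown, make it descriptive only, emphasise Grade 3+ AEs and SAEs, and allow for repeated events within participants in its interval. Note beside it that visits and tests are more frequent off ART and that Schedule 3 always follows ATI.

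The cost is a few extra table shells, some programming and the need to carry the ascertainment caveat. No new data or visits are needed: the dates come from the start of ATI and the start of Schedule 3.

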4.2.5.2 Local laboratory values

Box plots of local laboratory values will be generated for baseline values and for values measured during the course of the study by treatment arm and visit. Each box plot will show the first quartile, the median, and the third quartile. Outliers (values outside the box plot) will also be plotted. If appropriate, horizontal lines representing boundaries for abnormal values will be plotted.

For each local laboratory measure, summary statistics will be presented by treatment arm and timepoint, as well as changes from baseline for postenrollment values. In addition, the number (percentage) of participants with local laboratory values recorded as meeting Grade 2 AE criteria or above as specified in the Division of AIDS Table for Grading the Severity of Adult and Pediatric Adverse Events will be tabulated by treatment arm for each timepoint after initiation of treatment interruption. Reportable clinical laboratory abnormalities without an associated clinical diagnosis will also be included in the tabulation of AEs described above.

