6.5 Primary safety analysis

AEs and SAEs

AEs will be summarized using Medical Dictionary for Regulatory Activities (MedDRA) System Organ Class and preferred terms. Tables will show by treatment arm the number and percentage of participants experiencing an AE within a System Organ Class or within preferred term category by severity or by relationship to treatment interruption. For the calculations in these tables, a participant with multiple AEs within a category will be counted once under the maximum severity or the strongest recorded causal relationship to treatment interruption. Formal statistical testing comparing arms is not planned since interpretation of differences must rely heavily upon clinical judgment.

Local laboratory values

Box plots of local laboratory values will be generated for baseline values and for values measured during the course of the study by treatment arm and visit. Each box plot will show the first quartile, the median, and the third quartile. Outliers (values outside the box plot) will also be plotted. If appropriate, horizontal lines representing boundaries for abnormal values will be plotted.

For each local laboratory measure, summary statistics will be presented by treatment arm and timepoint, as well as changes from baseline for postenrollment values. In addition, the number (percentage) of participants with local laboratory values recorded as meeting Grade 2 AE criteria or above as specified in the Division of AIDS Table for Grading the Severity of Adult and Pediatric Adverse Events will be tabulated by treatment arm for each timepoint after initiation of treatment interruption. Reportable clinical laboratory abnormalities without an associated clinical diagnosis will also be included in the tabulation of AEs described above.

Reasons for discontinuation of ATI and early study termination

The number and percentage of participants who discontinue ATI and who terminate from the study early will be tabulated by reason and treatment arm.

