10.2 List of Figures

These graphs are included in the DSMB reports and FSR for Safety:

- Longitudinal Summaries of HIV-1 RNA Viral Load and CD4+ T-Cell Count (participant level) – all participants
- Longitudinal Summaries of HIV-1 RNA Viral Load and CD4+ T-Cell Count, restricted to participants who entered schedule 2 and to schedule 1 and 2 data points
- Cumulative Incidence of Meeting ART Re-Initiation Criteria
- Survival Plot of Time to Viral Load ≥ 200 (copies/ml)

Additional graphs included in FSR for Safety:

- Boxplots for local laboratory value (ALT, Direct Bilirubin, eGFR, Hemoglobin, Platelets, Absolute Neutrophil Count) at schedule 1 (visit 4, 8, 12, 14, 16, 18, 20, 21, 22, 23, 25, 27), schedule 2 (visit 40, 44, 48, 50, 52, 54, 56, 58, 60, 62, 64, 66), and schedule 3 (82, 84, 86, 89, 91)

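### The Grade 2+ laboratory table ignores each participant's grade before interruption, so it cannot separate abnormalities already present from those that emerge during ATI

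*Protocol*

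**What the plan says.** Laboratory measures are part of primary endpoint 2, under the objective of evaluating the safety of ATI (Protocol 3.2.1).

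Protocol 4.2.5.2 defines one graded laboratory table. It gives the number and percentage of participants with "local laboratory values recorded as meeting Grade 2 AE criteria or above as specified in the Division of AIDS Table". SAP 6.5 has the same rule: the counts "will be tabulated by treatment arm for each timepoint after initiation of treatment interruption". SAP 10.1 lists the output as "Local Laboratory Values Meeting Grade 2 AE Criteria or Above", among the tables added for the Final Study Report.

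The same protocol section also provides:

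- "Box plots of local laboratory values will be generated for baseline values and for values measured during the course of the study", with outliers plotted. SAP 10.2 includes Visit 4 (Day 0) in these plots for all six analytes.
- Summary statistics by arm and timepoint, "as well as changes from baseline for postenrollment values".
- Entry of reportable laboratory abnormalities that have no clinical diagnosis into the AE tables, which Protocol 4.2.5.1 breaks down "by severity or by relationship to treatment interruption".

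**The concern.** A Grade 2+ count restricted to visits after an intervention is naturally read as a description of what happened under that intervention. Here the rule does not ask whether the grade is new or worse than before, and it starts after the only visit that would show the starting position. A participant who begins ATI at Grade 2 and never changes adds one to the count at each later laboratory visit.

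In a trial with a group continuing ART, such carry-over would appear on both sides and could be discounted. This trial has no such group: everyone interrupts ART, and the arms differ only in past VRC01 or placebo. The comparison that bears on ATI is therefore within participant, before against during. The graded table, which is the display closest to counting people with abnormal results, does not make that comparison.

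**Working it through.** Section 4.2.5.2 states no figure to reproduce. The check is a reading of the rule, with simple arithmetic to show what a cell of the table can mean.

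**1. Which visits the table covers.** SAP 10.2 lists the box-plot visits for these analytes: 12 in Schedule 1 (Visit 4 is Day 0, so 11 follow it), 12 in Schedule 2 and 5 in Schedule 3. Read literally, timepoints after the start of interruption include the 5 Schedule 3 visits, when the participant is back on ART, and exclude Day 0.

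**2. Whether a participant can start ATI with an abnormal value.** Protocol 5.1 admits hemoglobin from 10.0 g/dL, ANC from 750 cells/mm³, platelets from 100,000 cells/mm³, ALT below 2.5 times the upper limit of normal, and eGFR above 60. Direct bilirubin must be normal, and exclusion 13 removes clinically significant abnormal results. Whether the remaining room reaches Grade 2 depends on cut-offs that the documents do not reproduce. These limits apply at screening. Appendix K lets screening precede Day 0 by up to 56 days, or 140 days for participants who switch from an NNRTI. Protocol 6.1.3 draws hematology and chemistry at the ATI qualification visit but sets only viral suppression as a laboratory-result condition there. A value can therefore change before interruption begins.

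**3. What a cell can mean.** Suppose 3 of 16 participants are at Grade 2+ at some visit. The cell is the same if 3 were carried over and 0 are new, if 0 were carried over and 3 are new, or for any split between. The table gives nothing with which to choose.

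**4. Possible size, by assumption only.** Let b be the share who begin ATI at Grade 2+ on a given analyte or set of analytes. The documents give no value for b, and zero is possible. For n participants the expected number is n × b, and the chance of at least one is 1 − (1 − b)^n. The n values are the ends of the planned range, 16 to 61.

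| Assumed b | Expected of 16 | Chance of ≥1 of 16 | Expected of 61 | Chance of ≥1 of 61 |
|---|---|---|---|---|
| 0% | 0 | 0% | 0 | 0% |
| 2% | 0.3 | 28% | 1.2 | 71% |
| 5% | 0.8 | 56% | 3.1 | 96% |
| 10% | 1.6 | 82% | 6.1 | 99.8% |
| 20% | 3.2 | 97% | 12.2 | about 100% |

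These are numbers starting ATI at Grade 2+. How many are counted later depends on whether the abnormality persists and on who is still in Schedule 1 or 2.

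**5. Effect of departures.** The planning median time to re-initiation criteria is 15.6 weeks (Protocol 4.1.1). Suppose 2 of 16 have a fixed abnormality and stay, 8 of the others move to Schedule 3, and the denominator is participants seen at the visit (the plan does not state it). The percentage then rises from 2/16 = 12.5% to 2/8 = 25% although nobody's value changed. This too is an illustration.

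**6. Whether the other displays recover the information.** Box plots show the distribution at each visit but do not link one participant's values across visits. Change-from-baseline statistics average over participants and do not count crossings of a grade. The AE tables show the recorded relationship to interruption, which is a judgement about an event and not a comparison of grades.

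**7. Baseline is undefined.** Under Protocol 6.1.2, participants who switch are enrolled on the first day of the new regimen and the others on Day 0. A change from baseline for postenrollment values could therefore start from different points in the two groups.

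**The case against.** The strongest reply is that the table is descriptive and assigns no cause. Attribution to ATI sits in the AE tables, and SAP 10.1 lists a separate table of ATI-related events. No formal testing between arms is planned for safety. Baseline values and changes appear in the same section, and the Grade 2+ table is not in the list for DSMB reports, so interim monitoring does not rest on it. All of this stands, and it makes the point small. It does not supply the missing count of participants who worsened.

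Three stronger readings are tempting, and the documents do not support them:

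- A reader might infer that pre-existing abnormalities will be reported as laboratory toxicity of ATI. Nothing in either document labels the table that way.
- A reader might cite Protocol 11.2.3, where "eGFR is required to be reported as an AE only if it is gradable per reported value or if dialysis is needed", as making the laboratory table count stable abnormalities. That section sets exceptions for AE reporting. It grades creatinine against the upper limit of normal, and creatinine is not among the six plotted analytes.
- A reader might add the 3% event rate quoted in Protocol 2.4 to an entry prevalence and obtain an inflated count. That 3% is an overall adverse-event rate during ATIs longer than 4 weeks, not an incidence of new Grade 2+ laboratory values at a timepoint.

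It is also fair to object that Day 0 is not the only reference: the same analytes are measured at screening and, for those who switch, at the switch and qualification visits. The accurate statement is that the participant's pre-ATI values together are the reference.

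**Conclusion.** The concern holds as a gap in the table specification. As written in both documents, the Grade 2+ table mixes abnormalities present before ATI with those that emerge during it, and no listed output separates them by participant. That conclusion follows from the text and needs no assumption about prevalence.

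The size is unknown. It rests on cut-offs and entry values that the documents do not give, and it may be zero for some analytes. Direct bilirubin is the least likely to be affected, since it must be normal at screening. Severity is minor: sample size, power, alpha and the primary virologic analysis are unaffected.

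**What to change.** In Protocol 4.2.5.2 and SAP 6.5 and 10.1:

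1. Define laboratory baseline as the last value on or before Day 0, for switch and non-switch participants alike.
2. Add a baseline column to the Grade 2+ table, and add a shift table from baseline grade to worst grade during ATI (Schedules 1 and 2).
3. Count participants whose grade is 2 or higher and above their own baseline grade, and state the denominator at each timepoint.
4. Show Schedule 3 visits separately, since participants are then on ART.
5. Keep the unrestricted count as a listing.

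The cost is table programming and wording. No new data are needed: hematology and chemistry are already drawn at Visit 4 (Protocol Appendix E).
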